Methods: The study conforms to the Consolidated Standards of Reporting Trials recommendations. Ethical approval will be sought from the University Health Network (UHN) Research Ethics Board. This proposed study is a single centered, factorial, randomized placebo-controlled trial with two independent variables, depth of capsaicin application and dose of capsaicin, for a total of four treatment arms and two control treatment groups.

Discussion: This will be the first study that assesses the B-mode ultrasound image texture of induced sensitized muscles, and will provide more evidence on muscle motor unit activity and regional changes of central sensitization. Findings from this study may support one of few hypotheses proposed delineating the involvement of central sensitization in the development of trigger points.

Trial Registration: Name: National Institutes of Health ClinicalTrials.gov.
Identifier: NCT03944889
Date of Registration: May 07 2019
URL: <https://clinicaltrials.gov/ct2/show/NCT03944889>

Keywords: myofascial pain syndrome; ultrasound; image texture; electromyography; central sensitization; trigger points

List of Abbreviations:

US: Ultrasound

EMG: Electromyography

MPS: Myofascial pain syndrome

MTrP: Myofascial trigger points

SEA: Spontaneous endplate activity

Background

Myofascial pain syndrome (MPS) is a prevalent chronic pain disorder primarily characterized by myofascial trigger points (MTrP). MTrP are stiff taut bands of muscle distinguished by hypersensitivity on palpation and local twitch responses on snapping palpation.[1] A current clinical challenge in chronic pain care, applicable to myofascial pain, is early detection and effective treatment targeting the underlying pathophysiology.

There is limited knowledge on the pathophysiology and mechanisms underlying MTrP and its development. Ultrasound studies have been able to characterize trigger points[32,45,46], however there are some contradictory findings on whether these areas are hyperechoic or hypoechoic[45,46]. More recently, texture feature analysis have been shown to differentiate between healthy and MPS as well as active and latent trigger points[32]. Trigger points are typically located within the region of the muscle belly, where there is a high distribution of motor endplates.[2,3] Seventy-one percent of acupoint locations in the body, which are regions associated with motor points, motor endplates, or major motor nerve pathways overlap with common MTrP.[4]

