- e. Is there a location dependent EMG response to capsaicin induced sensitization? In other words, do the texture features or EMG responses from muscles that lie anatomically distant from the location of the site of intramuscular capsaicin injection have changes from their baseline calculations? This would test the hypothesis that type III and IV afferents have an influence on the anterior horn cells that lie distant to the ones that are supplying muscle fibers in the vicinity of the stimulated sensory afferents.
- f. Is there a dose dependent EMG response of motor units to capsaicin induced sensitization? Here, the hypothesis of causality will be assessed in a preliminary manner. If there is a relationship then further experiments that more thoroughly assess causality will be needed.

Methods & Design

Study Design:

The study conforms to the Consolidated Standards of Reporting Trials recommendations.

Ethical approval is approved by the University Health Network (UHN) Research Ethics Board.

This study is registered under the National Institutes of Health ClinicalTrials.gov.

This proposed study is a single centered, factorial, randomized placebo-controlled trial with two independent variables, depth of capsaicin application and dose of capsaicin, for a total of nine treatment arms. The first between groups variable will be topical capsaicin application

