and injectable capsaicin injection. Within each partition there will be three treatments: control, 50 micrograms, 100 micrograms. One-hundred micrograms reported to be an effective high dose of capsaicin.[13] The control group will receive a topical skin lotion which is inert and has no sensitization effect. An equal number of participants will be allocated to each of the six treatment groups using an electronic randomization generator. Block randomization will be used to ensure equal allotment into each group. An alternate member of the research team will conduct the randomization schedule a priori. Participant allocation will be concealed by placing their assignment in an envelope and delivered to participants by the same member of the research team uninvolved in the measurement or randomization protocols. Participants and investigators will be blinded to the delivered dose; however, the type of capsaicin delivery cannot be blinded from either participants or investigators. The member of the research team conducting the randomization schedule and concealing allocation will have knowledge of and keep track of the doses contained in the containers and vials of the topical and injectable capsaicin, respectively. They will deliver the appropriate dose to the team member implementing the experimental protocol to ensure there is blinding with respect to dose. This individual will not be involved in participant recruitment.

Participants

Recruitment

Participants will be recruited from UHN and the University of Toronto clinics, employees, volunteers, visitors, students, and external participants. UHN is a tertiary healthcare centre with eight hospitals located in Toronto, Canada and the University of Toronto is an academic institution with a main campus located in close proximity to the main UHN hospitals

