perform a gradually decreasing contraction to rest. This will be performed four times for each type of study intervention and before as well as after each intervention, namely topical control cream, topical capsaicin at 50ug and 100 ug, injection of the superior aspect of the superior fascia followed by intramuscular injection with these two concentrations of capsaicin. The placement of these latter will be verified by ultrasound guidance. The intramuscular needle will then be removed and participants will be bandaged and cared for appropriately by the expert physician performing the experiment. Following this, ultrasound pictures will be taken again from the same muscles mentioned previously. Participants will be re-examined to determine if there were any adverse effects from the experimental procedures. If any occurred, then these will be carefully managed by the medical members of the research team and recorded. Participants will be asked to remain at the lab for an additional 30 minutes to ensure they are well prior to leaving (Figure 2).

Central sensitization and measurement techniques

Inducing central sensitization

Central sensitization will be induced using capsaicin according to the established technique.[13,24,25] It induces increased pain severity at high doses relative to heat and elicits a dose dependent pain responses, allowing for more easily quantifiable measurements.[26] Capsaicin delivery induces both primary and secondary nociception suggesting that central mechanisms are involved in the nociceptive response, also termed as central sensitization.[13,14] Previous evidence has confirmed that capsaicin can sensitize nociceptive and mechanoheat receptors outside of the region of primary hyperalgesia, with speculation that it can also sensitize chemonociceptive receptors.[13] Therefore, capsaicin can effectively be used to induce central sensitization.

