Capsaicin will be applied directly to the region of the innervation zone at the muscle belly to sensitize the neurons within the region of taut band development. Topical and intramuscular capsaicin will be used. The capsaicin formula will be compounded by a registered pharmacist. Topical capsaicin will be delivered in a cream and injectable capsaicin will be intermixed with saline prior to injection. The control group in the topical capsaicin arm will be treated with the cream base used during the experiment without added capsaicin and the injection arm will be injected with saline. A trained medical professional on the research team will apply the topical capsaicin or topical placebo treatments. The region of topical application will measure 5cm squared in the dermatome zone location to cover an area of approximately 25cm². A trained physician in physical medicine and rehabilitation will deliver injectable capsaicin using a 27-gauge needle at the location of the superior fascia of the upper trapezius muscle with ultrasound guidance. The fascial layer was chosen as it is the region with the lowest pressure pain threshold relative to skin and muscle, suggesting a high density of nociceptors within the layer, and it possesses connections to the spinal cord.[27] Changes in muscle fascia properties and nociception at muscle fascia, compared to nociception at muscle or subcutaneous tissue, has also been implicated in the development of pain.[28,29] Furthermore, intramuscular capsaicin will also be injected using ultrasound guidance to avoid the superior or inferior fascia.

To confirm the presence of central sensitization, brush allodynia will be used to detect mechanical hyperalgesia outside the region of primary nociception—region of topical placement or injection—which is the region of secondary hyperalgesia.[13-15] The size of the region of secondary hyperalgesia will be measured to characterize the extent of central sensitization. This will be accomplished using a tape measure and the perpendicular dimensions of the region of secondary hyperalgesia will be recorded in square centimeters.

Ultrasound analysis

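### The capsaicin-free control is described inconsistently: saline is the likely control for injection, but two sections name only a topical control and the group counts do not settle it

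*Combined protocol and SAP*

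**What the plan says.** Three parts of the protocol describe the control, and four give a number of groups.

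**The control**
- Study Design, on the two routes: "Within each partition there will be three treatments: control, 50 micrograms, 100 micrograms". This implies a control for injection as well as for topical application.
- Study Design, shortly afterwards: "The control group will receive a topical skin lotion which is inert and has no sensitization effect". No injected control is named.
- Experimental Protocol lists the interventions before and after which contractions are recorded: "namely topical control cream, topical capsaicin at 50ug and 100 ug, injection of the superior aspect of the superior fascia followed by intramuscular injection", with the injections given at the two capsaicin concentrations. Saline does not appear.
- Inducing central sensitization says that topical controls are "treated with the cream base used during the experiment without added capsaicin and the injection arm will be injected with saline". It also says that "injectable capsaicin will be intermixed with saline prior to injection", so saline is the injection vehicle.

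**The number of groups**
- Abstract, Methods: "for a total of four treatment arms and two control treatment groups", that is, six.
- Study Design, opening: "for a total of nine treatment arms".
- Study Design, randomisation: "An equal number of participants will be allocated to each of the six treatment groups".
- Sample size calculation: seven groups, not named, with two measurements each.

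**The concern.** A reader working from Study Design's lotion sentence and the Experimental Protocol list would set up a topical control only. Two things would follow for the injection groups.

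- **Confounding.** Injected capsaicin would be compared with a group that had no injection. The difference would contain the drug effect plus any effect of the needle and the injected fluid. The EMG outcomes, which are primary, are recorded in the trapezius, the muscle that is injected.
- **Blinding.** Study Design accepts that route cannot be blinded and relies on blinding of dose. With no zero dose among injected participants, everyone who had an injection would be known to have received active drug.

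Research question f (dose response) would also lose its zero-dose anchor within the injection route, and the two-factor layout would have an empty cell.

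There is a smaller mismatch on the topical side. Study Design speaks of an inert lotion, whereas the later section specifies the trial's own cream base. The matching base protects the dose blind better.

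**Working it through.** The plan gives no figure for this point, so the check compares the texts and counts groups.

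**1. Which control does each section support?**

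| Section | Topical control | Injected control |
|---|---|---|
| Abstract, Methods | two controls, content not given | implied by two controls |
| Study Design, treatments per route | yes | yes |
| Study Design, lotion sentence | lotion | none named |
| Experimental Protocol, list | cream | none listed |
| Inducing central sensitization | cream base | saline |

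The most specific text and both structural statements favour saline. One sentence conflicts with it, and the procedural list omits it.

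**2. Do the group counts decide it?**

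- List as written, fascial then intramuscular injection in the same person: 1 + 2 + 2 = 5. With one saline group: 6.
- List as written, fascial and intramuscular as separate groups: 1 + 2 + 2 + 2 = 7. With one saline group: 8. With one per site: 9.
- Two routes × three levels = 6, which needs one injected control and matches the Abstract and the randomisation text.
- Three sites × three levels = 9, which needs two injected controls and matches the opening of Study Design.
- The seven groups of the sample size equal the separate-site list with no saline.

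So six and nine point to saline, and seven fits a design without it.

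**3. How many participants are affected on the six-group plan?**

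84 / 6 = 14 per group. Injected capsaicin: 2 × 14 = 28. Injected controls: 14 if saline is used, 0 if the lotion sentence and the list are followed.

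**4. Precision under each count**

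Assumptions: equal SDs before and after, the plan's correlation of 0.5, and 20% loss from 84 recruits. SD of change = √(2(1 − 0.5)) = 1 SD. The SE for one arm versus one control is √(2/n).

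| Groups | n per group after loss | SE (in SDs) |
|---|---|---|
| 6 | 84 × 0.8 / 6 = 11.2 | 0.42 |
| 7 | 84 × 0.8 / 7 = 9.6 | 0.46 |
| 8 | 84 × 0.8 / 8 = 8.4 | 0.49 |
| 9 | 84 × 0.8 / 9 = 7.5 | 0.52 |

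**5. Would the sample size support six groups?**

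This takes the group-by-time test with m = 2, ρ = 0.5, α = 0.05 and 80% power. It assumes that the stated effect of 0.5 means f = 0.5/2 = 0.25. Then λ = f²Nm/(1 − ρ), with (k − 1)(m − 1) and (N − k)(m − 1) degrees of freedom. In equal groups this needs 63 participants for seven groups, against the plan's 70, which is therefore not reproduced exactly. It needs 60 for six groups and 72 for nine. Expected completers are 84 × 0.8 = 67.2, which is enough for six and short for nine.

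**The case against.** The strongest reply is that the section on inducing sensitization answers the question. It assigns controls by route, it is the most specific text, and it agrees with the two controls in the Abstract and the control in each route in Study Design. On this view only the lotion sentence conflicts, and the Experimental Protocol list, which is about when contractions are repeated, is merely silent. Most of this stands, and it is why saline is taken here as the likely intent. But that list is also the operational account of what is given, and it gives injections only at the two capsaicin concentrations.

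Other points limit the harm:
- Texture images are to be taken away from tissue affected by the needle or injection. This does not protect the EMG outcomes.
- The EMG needle is not specific to the injected groups, so it does not add to the confounding.
- The 50 versus 100 microgram comparison within a route keeps its comparator and its blinding either way.
- Capsaicin pain depends on dose, and hyperalgesia is measured before outcomes. Blinding of active against inert would be imperfect even with saline.
- Figure 1, the flow chart, is not available here and may name the arms. It could not remove the conflict between the written sections.

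A reader might infer that the trial has no injected control, or that the seven groups prove none was planned. The documents do not support either reading: saline is assigned explicitly in one section, and the sample-size text names no groups. Nor can a reader infer that the counts all confirm saline, since seven fits a list without it.

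**Conclusion.** The inconsistency is real and should be corrected before enrolment. It is an unclear specification with a likely sound intent, and it does not show a flawed control. If saline is given to injection controls, the confounding and the loss of zero-dose blinding do not arise. If the lotion sentence and the intervention list are followed, 28 participants on injected capsaicin would have no injected control in place of 14, assuming the six-group plan and equal allocation of 84. The documents give no basis for the size of the resulting bias, and no false-positive rate is claimed.

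**What to change.** 1. In Study Design, replace the lotion sentence with route-matched controls: cream base for topical, and saline at the same site and volume, from coded vials, for injection.
2. Add the saline injection to the list in Experimental Protocol, and call the topical control cream base throughout.
3. Use six groups (two routes × three levels) in the Abstract, Study Design and Sample size calculation, list them by name, and restate the sample-size basis for six. State that fascial and intramuscular injection are given in sequence to the same participant, if that is the intent.
4. Revise Determination of Central Sensitization. As written, it withdraws anyone not sensitized after a second application, which would remove cream and saline controls alike. Keep all randomised participants in measurement and analysis, and record sensitization status. Any second application should use the participant's own coded preparation. Exempting controls alone would reveal allocation to staff who are blinded to dose.

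**Cost.** On the six-group plan, items 1 to 3 are wording: saline is already the vehicle, and 84 / 6 = 14 per group needs no extra recruits. Saline controls would undergo an injection. Item 4 changes a procedure, and the primary comparison would then include capsaicin participants who did not sensitize. If fascial and intramuscular injections are meant as separate groups, adding saline makes eight or nine groups, and the SE rises from 0.46 SD at seven to 0.49 or 0.52 SD at the same 84 recruits. That is a design trade-off for the sponsor and lies outside the core fix.

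### The plan gives six, seven and nine groups in different places and does not settle which injection site or control belongs to which arm

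*Combined protocol and SAP*

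**What the plan says.** **Number of arms.** The Abstract (Methods) counts four active arms plus two controls. Study Design first announces a factorial trial "for a total of nine treatment arms". It then defines two routes, topical and injectable, and says "Within each partition there will be three treatments: control, 50 micrograms, 100 micrograms". Finally it states "An equal number of participants will be allocated to each of the six treatment groups using an electronic randomization generator". Sample size calculation works with seven groups measured before and after.

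**What is given.** Experimental Protocol sets out the interventions as "namely topical control cream, topical capsaicin at 50ug and 100 ug", then "injection of the superior aspect of the superior fascia followed by intramuscular injection with these two concentrations of capsaicin". No saline injection is in that list. Of the ramp contractions it says "This will be performed four times for each type of study intervention and before as well as after each intervention".

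**Sites.** Inducing central sensitization places injectable capsaicin at the superior fascia, gives reasons for choosing that layer, and then says that capsaicin is also injected into the muscle while avoiding fascia. It ties neither site to an arm.

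**Controls.** Study Design says "The control group will receive a topical skin lotion which is inert and has no sensitization effect". Inducing central sensitization says the topical control gets the cream base and "the injection arm will be injected with saline".

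**Analysis.** Statistical analysis plan runs a repeated measures ANOVA of EMG with intervention group as the factor. It does not list the groups.

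**The concern.** A factor can be coded only if its levels are known, and here they are not. The six-group layout has one injectable route with its own control. The list in Experimental Protocol divides injection into two sites and names no injection control. A team following that list would run a different experiment from a team following Study Design together with Inducing central sensitization.

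Two consequences are conditional on how the text is read:

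- If fascial and intramuscular injection are two steps in one participant, their effects cannot be told apart. The amount received may also differ from the 50 or 100 microgram label. That bears on research question f, which asks whether the EMG response depends on dose.
- If saline is left out, as in the Experimental Protocol list, any texture or EMG change in the injection arms mixes capsaicin with injected fluid. Experimental Protocol itself recognises that a needle or injected substance can affect the muscle mechanically, since it asks for images away from that region.

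**Working it through.** **Step 1. Which layouts fit which count?** The documents do not list the arms behind seven or nine, so the last two lines are arithmetic fits, not documented layouts.

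- Two routes × three levels = 6. This fits the Abstract and the allocation sentence in Study Design.
- One topical control + two topical doses + two fascial doses + two intramuscular doses = 1 + 2 + 2 + 2 = 7. This is the Experimental Protocol list read as separate arms. It fits the sample size, but it has no saline arm.
- Three sites × three levels = 9. This fits the nine arms in Study Design.

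**Step 2. Does each reading agree with the rest of the text?**

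- *Six groups:* agrees with the saline control, but leaves the site or sites used in the injectable arms undefined and disagrees with the seven-group sample size.
- *Seven separate arms:* agrees with the sample size, but disagrees with six-group allocation and with the saline control.
- *Nine arms:* allows a control at each site, but disagrees with both six and seven.
- *Two injections in sequence in one participant:* compatible with the wording of the list and of Inducing central sensitization, but the dose label then has no defined total.

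No reading agrees with every section.

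**Step 3. The plan's own sample size.** Inputs from Sample size calculation: 7 groups, m = 2 measurements, correlation ρ = 0.5, power 80%, alpha 0.05, effect size 0.5 given as Hedges' g, minimum N = 70. My assumption is that g = 0.5 corresponds to Cohen's f = 0.25. For the group-by-time interaction:

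λ = f² × N × m / (1 − ρ), df1 = (k − 1)(m − 1), df2 = (N − k)(m − 1).

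At N = 70: λ = 0.0625 × 70 × 2 / 0.5 = 17.5. With k = 7, df1 = 6, df2 = 63 and power is 0.866.

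| Groups k | Minimum N | Balanced N | Power at 70 | Power at 84 | Per group at 70 / 84 |
|---|---|---|---|---|---|
| 6 | 58 | 60 | 0.891 | 0.948 | 11.7 / 14 |
| 7 | 62 | 63 | 0.866 | 0.932 | 10 / 12 |
| 9 | 69 | 72 | 0.814 | 0.898 | 7.8 / 9.3 |

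The stated 70 is not reproduced with seven groups. Other seven-group variants are further away: the within-participant test needs 34 and the between-group test 170. With 0.5 entered as f, the interaction, within and between tests need 21, 13 and 48. The nearest result is the nine-group interaction test, at 69. That does not show nine groups were used.

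**Step 4. Does the group count threaten this test?** No. At N = 70 the omnibus interaction test has power above 0.80 for all three counts under the stated assumption. The group count changes what is compared and how many participants stand behind each arm. Nor can 84 be split equally into nine groups.

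**The case against.** The strongest reply is that the trial is plainly parallel-group and only loosely written. Much of that stands.

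- A reader might infer from Experimental Protocol that every participant receives every intervention. The documents do not support this. Participants are allocated to groups, the sample size has one before and one after measurement, the ANOVA factor is intervention group, and no sequence, period or washout is described. Taken literally it would mean 7 × 2 × 4 = 56 contractions per participant, against 2 × 4 = 8 in a parallel arm. The list can simply run across groups.
- A reader might infer that injection has no control at all. Inducing central sensitization gives saline, and the Abstract counts two controls. The gap is an incomplete list and a lotion-only sentence, not an established omission. Needle insertion alone is also not peculiar to the injection arms, because an EMG needle is placed under the general procedure. Injected fluid is what differs.
- A reader might add the doses: 50 + 50 = 100 and 100 + 100 = 200 micrograms. That assumes the full labelled amount at each site. A total divided between sites would leave the label unchanged. The text states neither.
- The route factor in Study Design is topical versus injectable, and no research question compares fascia with muscle. Injecting both sites would leave the planned route contrast intact.
- Figures 1 and 2 are not reproduced in the text available here and may show the arm layout and timeline.

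What does not go away is the written conflict among six, seven and nine, the disagreement about the injection control, and the unassigned injection sites. A figure could show which layout was meant, but it would not make the sentences agree.

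**Conclusion.** The arm structure is wrong as written. Six, seven and nine cannot all be true, and the sections disagree on the injection control. As a result the levels of the intervention factor and the basis of the seven-group sample size are not settled. Depending on the count, 84 recruits give 14, 12 or about 9.3 per group.

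The inability to separate fascial from intramuscular effects, and any mismatch between label and amount received, hold only if the two injections are given in sequence to one participant. The size of that mismatch cannot be derived from the documents. Mixing with fluid effects holds only if saline is actually omitted. Neither should be read as an established feature of the trial.

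This is not a power shortfall for the omnibus interaction test. That statement rests on f = 0.25 and on the interaction being the test intended. No view is taken on which dose, site or sequence is right.

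**What to change.** Reconcile the Abstract, Study Design, Experimental Protocol, Inducing central sensitization and Sample size calculation into one arm table. For each arm, state:

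1. the injection site or sites, and whether these are alternatives or steps in one participant;
2. the total dose label;
3. the matching control, with the Experimental Protocol list and the lotion sentence in Study Design made consistent with the saline control already described;
4. whether any participant receives more than one intervention;
5. that the pre-intervention recording is taken before any capsaicin in that participant.

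Then, in Statistical analysis plan, code the intervention factor with exactly those levels. Make the capsaicin-versus-control contrast within route, and keep the planned dose and route comparisons. Restate the sample size for that group count, naming the ANOVA test used and the effect size entered.

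The cost is wording. The protocol is dated June 25, 2019 and Trial Status has recruitment starting in June 2019. If enrolment has begun, the sites, amounts and control actually given to each participant must also be recorded, because analysis cannot recover them later.
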